Effects of Sublingual and Transdermal Administration of Nitroglycerin for Coronary CT Angiography on Image Quality

NCT#: NCT02961946

Study protocol and statistical analysis plan

October 14, 2018

Methods

This study had a prospective, randomized controlled design conducted at a single, academic hospital and was approved by our institution's review board, which required signed consent. The study was HIPAA compliant and registered at the Clinical Trials Registry (#NCT02961946) with the title "Effects of Sublingual and Transdermal Administration of Nitroglycerin for Coronary CT Angiography on Image Quality".

Based on prior literature, we hypothesized that mean coronary artery diameter before and after nitroglycerin application would be 2.86 mm and 3.26 mm, respectively, with 13.8% vasodilation (13). We assumed an equivalence range of 3% and determined a type-I error of (0.05/3=0.017) for a 3-group comparison with 80% power. In total, 198 individuals and 66 individuals per arm were necessary for a 3-group comparison.

Coronary artery vasodilation was the primary outcome. Secondary outcomes included changes in vital signs and frequency of side effects after nitroglycerin application. The dependent variable was the method of nitroglycerin delivery which could be lingual, sublingual, or transdermal.

Patient Selection

We identified potential subjects from our clinical cardiac CT schedule and included those whose study required an ECG-gated non-contrast CT followed by CCTA acquisitions. Subjects with a history of coronary revascularization were included. Exclusion criteria were age under 18 years, known hypersensitivity to nitroglycerin, closed-angle glaucoma, use of phosphodiesterase type 5 inhibitors within 72 hours prior to the study, conditions associated with elevated intracranial pressure, hemodynamic instability, critical aortic

stenosis, systolic blood pressure below 90 mmHg, pregnancy or lactating female, women with a positive urine pregnancy test, and subjects unwilling or unable to consent to participation.

Study Workflow

The physician enrolling the subject to the study was blinded to the method of nitroglycerin administration. After obtaining informed consent, subjects were randomized (block randomization, block size=198) to one of three nitroglycerin delivery methods: (1) sublingual as a tablet (2x0.4 mg, Nitrostat, Pfizer Inc., NY), (2) lingual as a spray (2x0.4 mg, Nitrolingual, Pohl-Boskamp, Hohenlockstedt, Germany), or (3) transdermal as a patch (2x0.4 mg/h, Nitro-Dur, Merck&Co Inc., NJ). After assessing initial vital signs (heart rate, rhythm, and blood pressure), non-contrast CT was acquired. Subsequently, nitroglycerin was administered. Patches were placed on the upper chest, taking care to avoid body hair. The transdermal delivery method required an application time of at least 45 minutes, while lingual and sublingual nitroglycerin required 5 minutes application time before CCTA acquisition (Figure 1). After CCTA, the patches were removed, and the location was inspected for skin reaction, while spray and tablets did not require further interaction. Next, we remeasured vital signs and asked for symptoms of allergic-type reactions and if sublingual tablets had completely dissolved. Systolic blood pressure >180 mmHg or a drop of >10 mmHg compared to initial values required observation and followup until normalization. Finally, patients filled out a guery asking about side effects during the exam.

Image Acquisition

All individuals were scanned on a 128-slice dual-source CT (Somatom Definition Flash, Siemens Healthineers, Forchheim, Germany). Scan length was from carina to diaphragm and was extended if necessary. Scan parameters were as follows: non-contrast CT (prospectively-ECG-triggered at 350ms after the R wave, fixed 120kV, mA adjusted to body size, with a reference of 80 mAs [CareDose4D, Siemens Healthineers], 64x0.6mm collimation), CCTA (prospectively-ECG-triggered for heart rates <85 bpm, ≥85 bpm retrospectively-ECG-gated, with an acquisition window in late systole to early diastole (220-400 msec after the R-wave), 80-120kV with optimal kV [CarekV, Siemens Healthineers] and automatic mA selection based on the scout scan, reference 280 mAs, 64x0.6mm collimation). No beta-blocker was administered, as per our standard site practice.

Images were reconstructed using iterative reconstruction algorithm (strength level 3/5, Admire, Siemens Healthineers) with 0.6 mm slice thickness at 350ms for non-contrast images and 220-440ms (20ms intervals) for CCTA images. All studies were blinded as to the nitroglycerin delivery method. Coronary calcium scores (Agatston method) and severity of any coronary artery disease were assessed from the radiology reports.

Quantitative Analysis

A cardiovascular imaging-trained radiologist with six years of experience (X.X.)(anonymized) measured coronary diameters at seven locations (**Figure 2**) using a 3D-workstation (Aquarius v.4.4.12, Terarecon Inc., Foster City, CA). These locations were predetermined as: (1) proximal right coronary artery (RCA) 1.5 cm distal from the ostium; (2) mid RCA 1.0 cm proximal of the acute marginal branch; (3) distal RCA 1.0 cm

proximal of the bifurcation into posterior descending artery and right postero-lateral branch; (4) middle of the left main (LM); (5) proximal left anterior descending artery (LAD) 1.0 cm after LM bifurcation or, if less distance to the 1st diagonal branch, in the middle of the proximal LAD; (6) mid LAD 2.0 cm distal of 1st diagonal branch or if less distance to the 2nd diagonal branch, in the middle of mid LAD; and (7) left circumflex coronary artery 2.0 cm distal of the LM bifurcation. Positions were located in the non-contrast images and reaffirmed on CCTA images using a corresponding phase of the cardiac cycle. Locations with non-calcified or calcified plagues or unclear depiction of the coronary artery due to adjacent structures such as veins were avoided, and in those segments, the location of measurement was moved distally up to 1.0 cm from the original position while staying in the same coronary segment and avoiding bifurcations. If coronary diameters could not be measured at any of these positions, the location was excluded. We excluded stented or bypassed locations from measurements. All coronary diameters were measured twice at each location using short-axis views in an enlarged field-of-view and averaged using window width and level of 350 HU and 50 HU for non-contrast and 800 HU and 200 HU for CCTA images (Figure 2). Window settings were set based on preliminary measurements in 20 patients who underwent CCTA without nitroglycerin and therefore no diameter differences in non-contrast and CCTA images. Locations #1, #4, and #5 were defined as proximal-, locations #2 #6, and #7 as mid-, and location #3 as distal coronary segments.

Safety

By query, side effects were evaluated, including headache, dizziness, and nausea during the exam. The severity of headache was quantified on a 10-point scale ranging from 1 minimal- to 10 maximal-intensity.

Statistical Analysis

Demographic and scan parameter summaries were calculated for the entire subject cohort and by nitroglycerin administration method. Categorical variables were summarized using frequencies and percentages, while continuous variables were summarized as means and standard deviations, or as median and interquartile range (25^{th} and 75^{th} percentiles) if the distribution of the variables were skewed. Differences in continuous variables by treatment were assessed using the Kruskal-Wallis test, and differences in categorical variables were assessed using either the Pearson χ^2 test, or Fisher's exact test. Changes of vital parameters pre- and posttreatment were compared using paired t-test.

A linear quantile (median) mixed-effects model was constructed to quantify the unadjusted association between treatment and vasodilation (contrast diameter/non-contrast diameter x 100) while accounting for dependencies within the data set due to multiple observations per subject. This modeling approach permitted the estimation of the median vasodilation as a function of covariates while avoiding the parametric modeling assumptions that are typically associated with linear mixed models. Estimates of fixed-effects, and their 95% Wald-type confidence intervals, were computed for all model

parameters. Linear combinations of these parameters were used to estimate overall effects, and effects by treatment.

Two additional models were constructed where we hierarchically accounted for patient demographics (i.e., age, gender, BMI and height) and then by patient demographics and disease severity measure (i.e., CA score). A subgroup analysis was performed where model parameters were estimated by proximal, mid and distal regions. Due to the explorative nature of this subgroup analysis, p-values were not adjusted for multiple comparisons.

All analyses were performed using R 3.4.3 (R-Core Team, 2017, Vienna, Austria) (20) and the lqmm R library (21).

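### Does narrating the initial vital signs after randomisation let the low-blood-pressure exclusion and the vital-sign baseline be decided with the arm known?

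*Combined protocol and SAP*

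**What the plan says.** Study Workflow gives the allocation step as "After obtaining informed consent, subjects were randomized (block randomization, block size=198) to one of three nitroglycerin delivery methods". The next sentence reads "After assessing initial vital signs (heart rate, rhythm, and blood pressure), non-contrast CT was acquired", and nitroglycerin follows the scan. This is the only pre-treatment blood-pressure reading described anywhere.

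Patient Selection, which precedes Study Workflow, lists among the exclusions "systolic blood pressure below 90 mmHg, pregnancy or lactating female, women with a positive urine pregnancy test". It does not say when the pressure is checked or from which reading.

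The initial reading has two stated uses. It is the reference for the observation rule in Study Workflow, "a drop of >10 mmHg compared to initial values required observation and followup until normalization". It is also the pre-treatment value for a secondary outcome: Methods says "Secondary outcomes included changes in vital signs and frequency of side effects after nitroglycerin application", and Statistical Analysis says "Changes of vital parameters pre- and posttreatment were compared using paired t-test".

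Two statements cover blinding. Study Workflow says "The physician enrolling the subject to the study was blinded to the method of nitroglycerin administration", and Image Acquisition says "All studies were blinded as to the nitroglycerin delivery method". Neither mentions whoever takes the vital signs.

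**The concern.** Taken as a strict sequence, the workflow makes one reading, taken after allocation, do three jobs: apply the blood-pressure exclusion, supply the baseline for vital-sign change, and anchor the 10 mmHg rule. The three delivery methods cannot be mistaken for one another, and the waiting time differs (at least 45 minutes for the patch, 5 minutes for the others), so staff at the scanner may know the arm. Someone who knows it could, in principle, exclude borderline patients selectively or record the baseline differently. Selective exclusion would undo part of what randomisation protects, and an error in a baseline reading passes one for one into that patient's change. The plan also does not say how a patient found ineligible after allocation is handled, and it defines no analysis population.

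**Working it through.** **Order of steps.** The text fixes three things: randomisation came after consent, the vital signs came before the non-contrast scan, and the drug came after that scan. It does not say that the vital signs followed randomisation; that comes only from the order of the sentences. If the order of the text is evidence, it also places Patient Selection, with the pressure exclusion, before the whole workflow. The workflow is plainly not a full account of screening either: it leaves out the pregnancy test, the glaucoma check and the phosphodiesterase-inhibitor check, all of which are listed exclusions. The absence of a screening pressure from the same paragraph is weak evidence that none was taken. Figure 1 is not available to settle the matter.

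**Size of selective exclusion.** The documents give no blood-pressure distribution and no count of such exclusions, so every input here except the 90 mmHg limit and the 66 patients per arm is an assumption. Let baseline systolic pressure be normal with mean m and SD s, and let a = (90 − m)/s.

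- Share below 90 mmHg: Φ(a). Expected number per arm: 66 × Φ(a).
- Rise in the arm's mean baseline if all of them are removed: s × φ(a) / (1 − Φ(a)).
- Shift in the arm's mean change: absolute slope of change on baseline (assumed 0.2 to 0.5) × rise.

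| m, s (mmHg) | a | Φ(a) | Patients of 66 | Rise (mmHg) | Shift in mean change (mmHg) |
|---|---|---|---|---|---|
| 130, 18 | −2.22 | 0.0131 | 0.87 | 0.62 | 0.12 to 0.31 |
| 120, 20 | −1.50 | 0.0668 | 4.41 | 2.78 | 0.56 to 1.39 |
| 140, 15 | −3.33 | 0.0004 | 0.03 | 0.02 | 0.005 to 0.01 |

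This is a worst case. It needs every low reading removed in one arm and every one kept in the other two, against the stated criterion. It also ignores the separate exclusion for hemodynamic instability, which would already remove some of these patients. The largest shift, 1.39 mmHg, is about a seventh of the plan's own 10 mmHg threshold.

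**Cost in power.** The plan's 66 per arm (3 × 66 = 198) cannot be reproduced, because no SD is stated. Suppose instead that the plan has exactly 80% power at 66 per arm, using two one-sided tests at α = 0.05/3 and a margin of 3 percentage points. The implied SD is 3 × √(66/2) / (2.128 + 1.282) = 5.05 points. Power at n per arm is then 2Φ(3 / (5.05 × √(2/n)) − 2.128) − 1. Losing about one patient per arm (the middle assumption) gives 79.1% at 65. Losing about four per arm (the extreme assumption) gives 76.1% at 62. These figures apply only if such patients were allocated, dropped and not replaced, none of which the documents report.

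**Baseline measurement.** The reading precedes nitroglycerin, so the drug cannot influence it. Only an observer effect remains, and the documents offer nothing from which to size it.

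**The case for a change.** The best argument for acting is that, on the documents alone, the only reading that could apply the pressure criterion is described after allocation. The blinding statements do not reach the person who takes it, and releasing the assignment after the initial vital signs would need no extra measurement. Part of this stands: the timing of the eligibility check is not stated, and neither is the handling of a patient found ineligible after allocation.

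The rest does not carry. The link between the exclusion and that reading is supplied by the reader, not by the text. For selective exclusion to occur, someone other than the blinded enrolling physician would have to make the decision knowing the arm, and the documents describe no such person or case. Later release would protect only half of the vital-sign change. The post-treatment reading follows patch removal and skin inspection and is taken alongside the question about tablet dissolution, so the arm may well be known by then whatever was done earlier. Later release also has a cost, because the patch arm's long slot would be known later on the scan day. Finally, the document is written in the past tense, as an account of a study already carried out, so a changed release time does not fit it.

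**Conclusion.** The observation about sentence order is accurate, but it shows an unstated time for the eligibility check, not a procedure that gives a wrong result. A baseline taken before the drug remains a valid baseline even if allocation came first. No route to bias in the primary outcome is shown. For vital signs, the worst-case shift is 0.1 to 0.3 mmHg under the middle assumptions and at most 1.4 mmHg at the extreme. Those figures rest wholly on the assumed pressure distribution and slope, so they are illustrative only. Trial staff would ordinarily confirm eligibility before allocation, and analysts would report any later exclusion by arm with its reason. A sentence giving the actual order would be a courtesy to the reader and would not alter any conclusion. No change is needed.

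### The post-dose blood-pressure rule has no absolute low limit, so a patient who starts at 90–99 mmHg systolic can finish at 80–89 mmHg without required observation (a narrow gap)

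*Combined protocol and SAP*

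**What the plan says.** All three arms receive nitroglycerin. Three places in the combined document bear on low blood pressure.

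- **Patient Selection** lists "systolic blood pressure below 90 mmHg" among the exclusions, so a patient at exactly 90 mmHg may be dosed. Hemodynamic instability is also an exclusion. Both apply at entry.
- **Study Workflow** takes a baseline before dosing: "After assessing initial vital signs (heart rate, rhythm, and blood pressure), non-contrast CT was acquired". After the CCTA it repeats the measurement: "Next, we remeasured vital signs and asked for symptoms of allergic-type reactions". It then gives the action rule: "Systolic blood pressure >180 mmHg or a drop of >10 mmHg compared to initial values required observation and followup until normalization".
- **Safety** covers symptoms: "By query, side effects were evaluated, including headache, dizziness, and nausea during the exam". It attaches no blood-pressure limit and no action to the answers.

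Methods names changes in vital signs as a secondary outcome, and Statistical Analysis compares them before and after treatment. Neither section sets a limit for an individual patient.

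**The concern.** The rule is absolute at the top and only relative at the bottom. A relative limit protects least those who start lowest. A patient who goes from 150 to 139 mmHg has fallen by 11 and must be observed. A patient who goes from 90 to 80 mmHg has fallen by exactly 10 and need not be, because the inequality is strict. Low pressure is a foreseeable effect of the drug in every arm, and the second patient is the one closer to hypotension.

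The entry limit and the observation rule do not contradict each other. The 90 mmHg figure decides who may be dosed and is not presented as a post-dose limit. The point is that the observation rule has no floor of its own.

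What is at stake is the care of a few patients on the day of the scan. Coronary vasodilation, the vital-sign and side-effect outcomes, and the sample size are untouched.

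**Working it through.** The plan states no figure to reproduce, so the check applies the written rule to every possible pair of readings.

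**Inputs**

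- Baseline systolic pressure *b* ≥ 90 mmHg (Patient Selection). I assume the reading that satisfies the entry limit is the same as the initial reading in Study Workflow; the document does not say so.
- Observation is required if the post-dose reading *p* > 180, or if *b* − *p* > 10 (Study Workflow).
- For the check, a low reading means *p* < 90. This value is borrowed from the entry limit.

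**Which readings escape**

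A low reading is untriggered when *p* ≤ 89 and *p* ≥ *b* − 10. Both can hold only if *b* − 10 ≤ 89, that is *b* ≤ 99. For each whole-number *b* from 90 to 99, the number of untriggered low readings is 89 − (*b* − 10) + 1 = 100 − *b*.

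| Baseline (mmHg) | Untriggered readings below 90 | Count |
|---|---|---|
| 90 | 80–89 | 10 |
| 91 | 81–89 | 9 |
| 92 | 82–89 | 8 |
| 95 | 85–89 | 5 |
| 98 | 88–89 | 2 |
| 99 | 89 | 1 |
| 100 or more | none | 0 |

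Over all ten baselines the total is 10 + 9 + … + 1 = 55 pairs. The lowest unobserved finish is 80 mmHg, reached only from 90.

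**What the rule already catches**

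- *b* ≥ 100 and *p* ≤ 89: the fall is at least 100 − 89 = 11, so it always triggers.
- *b* ≥ 90 and *p* ≤ 79: the fall is at least 90 − 79 = 11, so it always triggers.

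**Effect of a floor**

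With *p* < 90 added as a trigger, untriggered low pairs drop from 55 to 0.

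**Possible number of patients (assumptions, not from the documents)**

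Take baseline as normal and truncated below at 90. Take the fall as normal with mean *μ* and SD 10, independent of baseline. With *f* the baseline density before truncation, the expected number in the gap among 198 patients is

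198 × ∫ from 90 to 100 of *f*(*b*) [Φ((10 − *μ*)/10) − Φ((*b* − 90 − *μ*)/10)] d*b* ÷ P(baseline ≥ 90).

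| Baseline mean, SD | Mean fall | Expected patients of 198 |
|---|---|---|
| 120, 20 | 5 | 3.3 |
| 130, 18 | 10 | 1.1 |
| 140, 15 | 15 | 0.07 |

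These figures show scale only. The 55 pairs are combinations of readings and are not weighted by how likely each is.

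**The case against.** The strongest objection is that the gap exists only relative to a floor the review has chosen. Nothing in the documents says that 80–89 mmHg needs mandatory observation in someone who began at 90–99 and changed little. The size also depends on the floor. At 85 mmHg the untriggered pairs fall to 5 + 4 + 3 + 2 + 1 = 15, and the expected count under the same three scenarios falls to about 0.01–0.73 of 198. At 80 mmHg both are zero. This stands as a limit on the claim: 90 mmHg is a proposal, and the value is a clinical decision. It does not remove the fact that the rule has no floor at all.

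Second, the fall limit of more than 10 mmHg is already strict, vital signs are repeated in everyone, and staff may observe any patient they choose to. All true, and this is why the gap is narrow. But a written rule sets the required minimum, and for these patients it requires nothing once the low reading has been seen.

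Third, the two ranges should not be read as freely combined: a start of 99 can reach only 89 untriggered. That is correct, and the table by baseline shows it.

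Fourth, the document is written in the past tense, so enrolment may be finished and a new clause would then protect nobody. This also stands, and it is why the fix includes a reporting alternative.

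**Conclusion.** The concern holds. As written, the rule does not require observation for a patient with a baseline of 90–99 mmHg who falls by 10 mmHg or less to a reading of 80–89 mmHg. The missing lower limit and the bounds of the gap follow directly from the text, given that the initial reading meets the entry limit. How many patients are affected cannot be derived from the documents; about 0.07 to 3.3 of 198 is plausible under the assumed distributions, and none is possible. Whether 90 mmHg is the right floor is for the clinical lead. The point is a small safety improvement that should be made because it is cheap. It is not a threat to the trial's validity.

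**What to change.** In Study Workflow, add a third trigger to the observation rule: or a systolic blood pressure below 90 mmHg. Keep the action as it is, and have the clinical lead confirm the value.

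If enrolment is complete, report by arm, from the vital signs already recorded, how many patients ended below 90 mmHg without meeting the existing trigger.

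The cost is one clause and no new measurement, since post-dose vital signs are already taken in every patient. Under the assumptions above, about 0 to 3 of the 198 patients would be observed for longer. The retrospective count needs only the two systolic readings per patient.

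### CCTA tube voltage varies by patient under one fixed reading window, and no vasodilation model includes it; this may add between-patient noise to the primary ratio

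*Combined protocol and SAP*

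**What the plan says.** Image Acquisition fixes the non-contrast scan at 120 kV. The CCTA is acquired at "80-120kV with optimal kV [CarekV, Siemens Healthineers] and automatic mA selection based on the scout scan", so its voltage differs between patients.

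Quantitative Analysis has one radiologist measure diameters at seven locations, with the readings "averaged using window width and level of 350 HU and 50 HU for non-contrast and 800 HU and 200 HU for CCTA images". The same section explains the choice: "Window settings were set based on preliminary measurements in 20 patients who underwent CCTA without nitroglycerin", a group in whom the two scans should give equal diameters. The kV mix of those 20 patients and the residual error after calibration are not given.

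Statistical Analysis defines the outcome as "vasodilation (contrast diameter/non-contrast diameter x 100". The first model is unadjusted. Two further models add age, gender, BMI and height, and then the calcium score. Neither kV nor lumen attenuation appears in any of them. Summaries of scan parameters by delivery method are planned.

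The sample-size paragraph under Methods says "We assumed an equivalence range of 3" per cent. The images are masked for delivery method before reading.

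**The concern.** Iodine attenuates more at lower tube voltage, so the same vessel is brighter at 80 kV than at 120 kV. If the reader places the edge at or near a fixed grey level, a dim lumen reads too small and a bright lumen too large. The plan itself treats the window as something that affects measured diameter; otherwise it would not have needed calibrating. One calibration over 20 patients can centre the average error for their kV mix. It cannot centre the error at each kV.

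Voltage is fixed for the denominator and variable for the numerator, so any such error passes straight into the ratio. It belongs to the scan, so all seven locations of a patient share it and averaging over locations does not reduce it. Two things are at stake: the precision of the comparison between delivery methods, and the accuracy of the absolute vasodilation figure.

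**Working it through.** **The plan's own figures.** 0.05/3 = 0.0167 and 3 × 66 = 198 agree with the text. 3.26/2.86 = 1.140, or 14.0% against the stated 13.8%, a gap that does not matter here. The 66 per arm cannot be reproduced, because no SD is stated. Solving for the SD with two one-sided tests, true difference 0 and a margin of 3 ratio points:

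- n = 2[(z₁ + z₂) × SD/3]², with z₁ = 2.128 (one-sided 0.0167) and z₂ = 1.282 (80% power)
- SD = 3/3.410 × √(66/2) = 5.05 points

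A single one-sided test implies 5.8 points and a two-sided difference test 5.3. Three points of the ratio equal 0.03 × 2.86 = 0.086 mm. The plan does not say on which scale the 3% is meant.

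**How far the edge could move within a patient.** Every input here is an assumption except the 200 HU level and the 3.26 mm diameter. Take a Gaussian blur with s = FWHM/2.355, fat at −80 HU, and an edge read where the profile crosses 200 HU. The edge offset x solves L·Φ(−x/s) − 80·[1 − Φ(−x/s)] = 200, and the diameter error is 2x.

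| FWHM (mm) | Lumen 350 HU | Lumen 600 HU | Spread, % of 3.26 mm |
|---|---|---|---|
| 0.5 | −0.165 mm | +0.095 mm | 8.0 |
| 0.6 | −0.198 mm | +0.114 mm | 9.6 |
| 0.8 | −0.264 mm | +0.152 mm | 12.7 |

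The lumen values matter as much as the blur. With 420 and 500 HU at 0.5 mm blur, the spread is 0.082 mm, just under 0.086 mm.

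A wider grid used a blurred 3.26 mm disc, lumen 300–400 HU at 120 kV, surround −100 to 50 HU and blur 0.3–0.9 mm. Relative to 120 kV, the apparent diameter rises by:

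- 0.9–4.6% if attenuation rises by a factor of 1.1
- 1.6–8.3% for a factor of 1.2
- 2.5–12.8% for a factor of 1.35
- 4.1–20.4% for a factor of 1.7

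If the reader instead follows the half-height edge, the shift is about 0 throughout.

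**What this does between arms.** Suppose half the patients are at low kV and low kV shifts the ratio by d points. The chance difference between two arms has SE = d × √(0.5 × 0.5 × 2/66).

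- d = 5: SE 0.44 points. A 3-point arm difference would need low-kV shares 3/5 = 60 percentage points apart.
- d = 10: SE 0.87 points, 1.96 SE = 1.7. It would need shares 3/10 = 30 percentage points apart.

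**What this does to power.** The added between-patient SD is d/2. Take 5.05 as the planning SD and assume that it excludes this error.

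| d (points) | Added SD | Total SD | Power at 66 per arm | Per arm for 80% |
|---|---|---|---|---|
| 0 | 0 | 5.05 | 80% | 66 |
| 5 | 2.5 | √(5.05² + 2.5²) = 5.63 | 65% | 83 |
| 8 | 4.0 | √(5.05² + 4.0²) = 6.44 | 42% | 108 |

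These are normal approximations on one value per patient, not the planned median mixed model.

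**The case against.** The strongest defence is that the reader is not a threshold. An 800/200 window shows −200 to 600 HU as a grey ramp, and a trained radiologist on enlarged short-axis views may follow the half-height edge, in which case kV hardly matters. No edge rule is stated, so this cannot be excluded. It fits less well with a plan that had to calibrate its windows, but it stands as the lower end of the range.

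A reader might infer that kV moves the diameter by more than the equivalence range and so undermines the equivalence comparison. The documents do not support that. They give no lumen attenuation, resolution, kV distribution or edge rule, and the calculated shift falls on both sides of 3%. The comparison is also not like for like: the 3% belongs to the comparison of groups, while the kV shift acts within a patient. Delivery method is randomised, reading is masked, and kV is selected automatically from the scout, so no systematic difference between arms is expected. Pure noise makes equivalence harder to show; it does not favour a false claim of equivalence.

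The plan also offers partial protection. The calibration addresses the mean offset, BMI and height may stand in for part of kV in the adjusted models, and the scan-parameter summaries are a natural place to show kV balance. None of these covers the unadjusted model or shows that the window holds at each kV. Finally, the power loss depends on the planning SD excluding this error, which cannot be checked.

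**Conclusion.** The concern holds as a precision and calibration gap. Established from the documents: variable kV in the numerator scan only, one fixed CCTA window, a calibration not shown to hold by kV, and no kV term in any model. Not established: the size. It lies between about 0 and well above 3% of diameter within a patient, depending on assumed lumen attenuation, blur and edge rule.

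Bias in the randomised contrasts is not expected. If the shift were 5 points with half the patients at low kV, and if the unstated planning SD were about 5.05 and excluded this error, power would fall from 80% to about 65%. With a smaller shift, or with the error already in the SD, the loss would be less or nil. The absolute vasodilation level moves only if the trial's kV mix differs from that of the 20 calibration patients, on which there is no evidence either way. This is worth acting on because the remedy is nearly free, not because the comparison is shown to be compromised.

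**What to change.** Add CCTA tube voltage as a covariate in the two adjusted vasodilation models, or at least in a prespecified sensitivity model reported beside the unadjusted one. It is a setting of each scan, so it should be retrievable without new measurement, and because it comes from the scout and not from the delivery method, adjusting for it does not distort the treatment contrasts. Name kV among the scan parameters summarised by arm.

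The cost is one parameter if kV enters as linear or two levels, or two if three levels are used. It will overlap partly with BMI and height, so their coefficients should not be interpreted separately. The covariate captures brightness differences due to kV, not those due to contrast enhancement.

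Resetting the window for each patient is not recommended. The plan describes the measurements as done, so this would mean re-reading up to 198 × 7 = 1,386 CCTA locations, each twice. Re-checking the 20 calibration patients by kV would leave too few at each level to confirm a 3% tolerance.
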